4.3.1.5. Reduction in SARS-CoV-2 Viral Load

Viral load will be \log_{10} -transformed prior to summary and analysis. The Virology analysis set will be used for all analyses.

Reduction of SARS-CoV-2 viral shedding will be determined by the change from baseline of SARS-CoV-2 nasal viral load at Day 8.

In addition, the SARS-CoV-2 viral load will also be assessed from the area under the curve (AUC as determined by the trapezoidal rule) of \log_{10} -transformed SARS-CoV-2 viral load through Days 1 to 8. AUC will be log-transformed prior to analysis.

The proportion of participants with a persistently high SARS-CoV-2 viral load (PHVL) assessed by qRT-PCR at Day 8 will also be assessed. PHVL is defined as a viral load value $>4.1 \log_{10}$ copies/ml at Day 8.

4.3.1.6. Pharmacokinetics of VIR-7831

Serum pharmacokinetic concentrations will be listed and summarized by treatment and visit in the PK analysis set. Any concentration not included in summaries should be flagged in the individual listings with an explanation for the exclusion.

Additional PK analyses, including additional exposure-response analyses, will be summarized in a separate PopPK analysis plan.

4.3.2. Main Analytical Approach

4.3.2.1. Binary Endpoints

The following secondary endpoints will be summarised/analysed as binary endpoints:

- Participants who have progression of COVID-19 (emergency room, hospitalisation for any duration or cause, death) through Day 29
- Proportion of Participants Who Progress to Develop Severe or Critical Respiratory COVID-19 at Day 8, 15, 22 and 29
- Proportion of participants with a persistently high SARS-CoV-2 viral load at Day 8 by qRT-PCR

The secondary binary endpoints will be summarized using counts and percentages.

Participants who have progression of COVID-19 (emergency room, hospitalisation for any duration or cause, death) through Day 29 will be analysed as per the primary endpoint (hypothetical and treatment policy estimands).

4.3.2.2. Continuous Endpoints

The following secondary endpoints will be summarised/analysed as continuous endpoints:

- Change from baseline in viral load in nasal secretions by qRT-PCR at Day 8
- Area under the curve (AUC) of SARS-CoV-2 viral load as measured by qRT-PCR from Day 1 to Day 8 (AUC_{D1-8})
- Serum pharmacokinetic concentrations

Change from baseline in viral load at all visits including Day 8 will be summarised on the log10 scale. The Virology analysis set will be used.

AUC_{D1-8} for log10-transformed SARS-CoV-2 viral load will be analyzed using analysis of covariance adjusted for treatment group (sotrovimab 500mg IV, sotrovimab 500mg IM), baseline viral load, derived age group (<65 years old, ≥ 65 years old, see Section 6.2.7), and gender (female, male). AUC will be log-transformed prior to analysis. The treatment ratio and two-sided 90% CI for the comparison of sotrovimab 500mg IM vs sotrovimab 500mg IV will be calculated by back-transforming the corresponding estimates on the log-scale.

In addition, the following will be produced:

- Box plot of serum pharmacokinetic concentrations at Day 8, 15 and 29 vs COVID-19 progression status through Day 29 (as defined in section 4.2.1) for the hypothetical estimand, overall and by treatment group

- Summary table of Day 8 serum pharmacokinetic concentrations (n, mean, SD, median, min, max) by COVID-19 progression status through Day 29 (as defined in section 4.2.1) for the hypothetical estimand, total and by treatment group.

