1.1. Objectives, Estimands and Endpoints

Objectives	Endpoints
Primary	

 Evaluate the efficacy of two dose levels of intramuscular sotrovimab versus intravenous sotrovimab in preventing the progression of mild/moderate COVID-19 	
Progression of COVID-19 through Day 29 as defined by:
 
 Hospitalization > 24 hours for acute management of illness due to any cause OR Death
Secondary	
Safety 
 Describe the safety and tolerability of intramuscular and intravenous sotrovimab 	
 Occurrence of adverse events (AEs) Occurrence of serious adverse events (SAEs) Occurrence of adverse events of special interest (AESI) Occurrence of disease-related events

 Assess the immunogenicity of sotrovimab 	
 Incidence and titers (if applicable) of serum anti-drug antibody (ADA) to sotrovimab
Efficacy 
 Evaluate the efficacy of two dose levels of intramuscular versus intravenous sotrovimab on the progression of mild/moderate COVID-19 	
Progression of COVID-19 through Day 29 as defined by:
 
 Visit to a hospital emergency room for management of illness OR Hospitalization for acute management of illness for any duration and for any cause OR Death

Objectives	Endpoints

 Evaluate the efficacy of two dose levels of intramuscular versus intravenous sotrovimab in preventing COVID-19 respiratory disease progression 	
 Development of severe and/or critical respiratory COVID-19 as manifested by requirement for respiratory support (including oxygen) at Day 8, Day 15, Day 22, and Day 29

 Compare the virologic activity of sotrovimab given IM (two dose levels) or IV in reducing SARS-CoV-2 viral load 	
 Mean area under the curve of SARS-CoV-2 viral load in nasal secretions as measured by qRT-PCR from Day 1 to Day 8 (AUC_{D1-8}) Change from baseline in viral load by qRT-PCR at Day 8 Proportion of participants with a persistently high SARS-CoV-2 viral load at Day 8 by qRT-PCR

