2.1. Multiplicity Adjustment

Hypotheses (1) and (2) above will be tested using the primary estimand according to the hierarchical testing principal as follows:

- If the null hypothesis for (1) is rejected, i.e., the upper bound of the two-sided 95% confidence interval for the risk difference between sotrovimab 500 mg IM and

sotrovimab 500 mg IV is less than the pre-specified 3.5% non-inferiority margin, then hypothesis for (2) will be tested.

- If the null hypothesis for (1) is not rejected, then hypothesis for (2) will not be tested.

Below is a summary of possible outcomes of the hierarchical testing procedure:

Which Null Hypothesis is Rejected	Non-inferiority Declared For
Hypotheses (1) and (2)	Both sotrovimab 500 mg IM and sotrovimab 250 mg IM (vs. sotrovimab 500 mg IV)
Hypothesis (1) but Not (2)	Only sotrovimab 500 mg IM vs. sotrovimab 500 mg IV
Hypothesis (1) is NOT rejected (Null hypothesis for (2) won't be tested in this case)	Neither sotrovimab 500mg IM nor sotrovimab 250mg IM (vs sotrovimab 500mg IV)

Two secondary endpoints will be formally analysed:

- 1) Mean area under the curve of SARS-CoV-2 viral load in nasal secretions as measured by qRT-PCR from Day 1 to Day 8 (AUC_{D1-8}). Each IM dose will be assessed for equivalence to IV based on the two-sided 90% confidence interval for the treatment ratio falling within equivalence bounds of 0.5 to 2.0.
- 2) Progression of COVID-19 through Day 29 as defined by visit to a hospital emergency room for management of illness OR Hospitalization for acute management of illness for any duration and for any cause OR Death. Each IM dose will be assessed for non-inferiority vs IV using a non-inferiority margin of 3.5% on the risk difference scale.

The testing of the two secondary endpoints above is adjusted for multiplicity by using the following hierarchy:

- Secondary endpoint (1) will only be tested if non-inferiority is achieved for sotrovimab 500 mg IM vs. sotrovimab 500 mg IV and sotrovimab 250 mg IM vs. sotrovimab 500 mg IV comparisons for the primary endpoint.

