4. STATISTICAL ANALYSES

4.1. General Considerations

4.1.1. General Methodology

The ITT Analysis Set will be used for all Study Population analyses and Efficacy analyses, unless otherwise specified. A subset of the ITT analysis set will be used for the primary estimand, excluding participants who did not meet key inclusion/exclusion criteria (see 4.2.2). The Safety Analysis Set will be used for selected Study Population summaries and all safety analyses. The PK analysis Set will be used for all PK analyses. Virology analysis set will be used for all Virology analyses.

In the case of a difference between the stratification assigned at the time of randomization and the data collected in the eCRF, the analyses will be performed based on the data collected in the eCRF, not the assigned stratum at randomization. All analyses will be adjusted for treatment group (sotrovimab 500mg IV, sotrovimab 500mg IM), derived age group (<65 years old, ≥65 years old, see Section 6.2.7), and gender (female, male). Stratification factors of region and vaccination status are not included as covariates due to the small number of non-US and partially/fully vaccinated participants in the ITT analysis set. In addition the 12-17 years old and 18-64 years old categories are combined due to the small number of participants in the 12-17 years old category.

In the case of model convergence issues, if one category dominates within a particular covariate then that covariate may be considered for removal from the model.

Confidence intervals will use two-sided 95% confidence levels unless otherwise specified.

Unless otherwise specified, continuous data will be summarized using descriptive statistics: n, mean, standard deviation (std), median, minimum and maximum. For log-transformed data (e.g. AUC) descriptive statistics will present the geometric mean, standard deviation (SD of log-transformed data) and coefficient of variation. Categorical data will be summarized as the number and percentage of participants in each category.

Efficacy data will be reported according to nominal time of clinical visits unless otherwise stated. Hospitalization status, oxygen supplementation and healthcare resource utilization use will be slotted against the clinical visit date for summaries and analyses by visit.

All data will be reported according to the nominal time of clinic visits and assessments as specified in the protocol unless stated otherwise:

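### Day 8 change in viral load sits under an objective to compare IM with IV but gets only raw by-arm summaries; a baseline-adjusted difference with an interval would be a nearly free supportive addition.

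*SAP*

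**What the plan says.** SAP 1.1 places three secondary endpoints under the objective "Compare the virologic activity of sotrovimab given IM (two dose levels) or IV in reducing SARS-CoV-2 viral load". One is the AUC of viral load from Day 1 to Day 8, one is "Change from baseline in viral load by qRT-PCR at Day 8", and one is persistently high load at Day 8.

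SAP 4.3.2.2 treats the two continuous endpoints differently:

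- **Day 8 change:** "Change from baseline in viral load at all visits including Day 8 will be summarised on the log10 scale". SAP 4.1.1 defines what that means: "continuous data will be summarized using descriptive statistics: n, mean, standard deviation (std), median, minimum and maximum".
- **AUC:** it "will be analyzed using analysis of covariance adjusted for treatment group (sotrovimab 500mg IV, sotrovimab 500mg IM), baseline viral load, derived age group" and gender, and is reported as an IM/IV ratio with a 90% CI.

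Three other places bear on the point:

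- SAP 2.1 states "Two secondary endpoints will be formally analysed". These are the AUC and the progression endpoint that counts emergency room visits, hospitalization or death. Day 8 change is not one of them.
- SAP 4.1.3 sets results below the limit of detection or quantification to 1.78 log10 copies/mL.
- SAP 4.6.1 summarises change from baseline by visit within five bands of baseline viral load.

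**The concern.** The objective is comparative, but the plan for this endpoint yields two columns of descriptive statistics and leaves the reader to subtract one mean from the other. That subtraction is sensitive to baseline. With a floor of 1.78, a participant who starts at 3 log10 can fall by at most 3 - 1.78 = 1.22, and one who starts at 8 by 8 - 1.78 = 6.22. If one arm happens to start higher, it will tend to show the larger fall with no difference in drug effect. The stratification factors in SAP 1.2 (age, vaccination history, region) do not directly balance viral load.

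The general rule in SAP 4.1.1 does not close the gap. It says "All analyses will be adjusted for treatment group (sotrovimab 500mg IV, sotrovimab 500mg IM), derived age group" and gender; baseline load is not in that list, and a descriptive summary has no model to adjust.

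What is at stake is how clearly a secondary result can be read. Day 8 change is the only secondary virology endpoint that would give an IM-IV contrast directly in log10 copies.

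**Working it through.** **1. The plan's own figure.** The documents give no sample size, SD or correlation for viral load. The only sample-size figure is for the primary endpoint (SAP 5): 340 per arm, about 90% power, 2% in both arms, margin 3.5%, one-sided 2.5%.

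- n = (1.96 + 1.2816)² × 2 × 0.02 × 0.98 / 0.035² = 337 per arm, against 340 stated.
- Power at 340 per arm is 90.3%.

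The figure reproduces, but it is used here only to supply n. The size of the Virology set is not stated and may be smaller.

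**2. Formulas.** Let k = SD(Day 8) / SD(baseline) and ρ = correlation of baseline with Day 8, both on the log10 scale and both assumed.

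- Variance of the ANCOVA difference over variance of the raw-change difference = k²(1 - ρ²) / (1 + k² - 2ρk). At k = 1 this is (1 + ρ)/2.
- Share of a baseline difference carried into the raw-change difference = ρk - 1. The negative sign means the arm that starts higher shows the larger fall.

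**3. Precision.** How much wider the raw-change 95% CI is than the ANCOVA CI:

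| k | ρ = 0.2 | ρ = 0.5 | ρ = 0.8 |
|---|---|---|---|
| 0.75 | 53% | 39% | 34% |
| 1.00 | 29% | 15.5% | 5% |
| 1.25 | 17% | 6% | 0% |

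- Top-left cell: 0.5625 × 0.96 / (1 + 0.5625 - 0.30) = 0.428, and 1/√0.428 = 1.53.
- Bottom-right cell: 1.5625 × 0.36 / (1 + 1.5625 - 2.0) = 1.00. This needs a Day 8-on-baseline slope ρk of exactly 1, which is hard to reconcile with a floor that compresses Day 8 values.

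A simulation (4,000 trials, 340 per arm, k = 1) gave variance ratios of 0.61, 0.73 and 0.90 at ρ = 0.2, 0.5 and 0.8, against 0.60, 0.75 and 0.90 from the formula. Both estimators were unbiased.

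**4. Absolute size.** Assume SD 1.5 log10 at both times and 340 per arm. The SD of a chance baseline difference is 1.5 × √(2/340) = 0.115 log10.

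| ρ | Carried over by a 1-SD imbalance (log10) | Half-width, raw change | Half-width, ANCOVA |
|---|---|---|---|
| 0.2 | 0.8 × 0.115 = 0.092 | 0.285 | 0.221 |
| 0.5 | 0.5 × 0.115 = 0.058 | 0.225 | 0.195 |
| 0.8 | 0.2 × 0.115 = 0.023 | 0.143 | 0.135 |

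At 200 per arm the 1-SD imbalance is 0.15, and the carry-over is 0.12, 0.075 or 0.03.

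**5. With the floor built in.** A simulation assumed 250 to 340 per arm, baseline mean 6.5 and SD 1.3 to 1.7, Day 8 mean 3.2, slope 0.2 to 0.5, residual SD 1.1 and the floor at 1.78. The variance was 35% to 66% lower with ANCOVA, which makes the raw CI 24% to 71% wider (1/√0.65 and 1/√0.34). The upper end exceeds 53% because k falls below 0.75 in some of these settings. The grid in step 3 is therefore a range over stated assumptions, not a bound.

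**6. Whether the AUC already gives this information.** The AUC is taken on log10 load, so its minimum over the seven days from Day 1 to Day 8 is 1.78 × 7 = 12.46. The equivalence bound of 2.0 in SAP 2.1 then corresponds to an AUC at least 12.46 larger, that is, an average load at least 1.78 log10 higher (10^1.78, about 60-fold). The AUC ratio is adjusted, but it is a coarse scale for judging a difference in log10 copies.

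**The case against.** The strongest reply is that no planned comparison is damaged. SAP 2.1 confines formal analysis to two secondary endpoints, and SAP 4.3.2.2 assigns Day 8 change to summary only. There is no planned standard error to be too wide and no planned test to distort. The objective does receive a baseline-adjusted IM-IV estimate with an interval, through the AUC, which has its own estimand and a place in the hierarchy. SAP 4.6.1 lets a reader see how change depends on baseline. All of this stands.

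A reader might infer three stronger things, and the documents support none of them:

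- **That the virology comparison as a whole is unadjusted.** It is not; the AUC model includes "baseline viral load, derived age group" and gender.
- **That the raw difference is biased.** Under randomisation it is unbiased on average. The problem arises only given a chance imbalance in the realised trial.
- **That much of the precision is lost.** This depends on SDs and correlations that the documents do not give, and the assumed range includes no loss at all.

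What does not stand is that the existing outputs replace an adjusted estimate. Five baseline bands give no pooled IM-IV difference or interval, and the AUC ratio is not read in log10 copies.

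Timing also counts. The protocol supplied (Amendment 4) says that main-study enrolment finished on 19-AUG-2021 and quotes Day 29 results. A model added after that point is post hoc.

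**Conclusion.** The point holds as a modest gap. An endpoint under a comparative objective has no between-arm estimate, interval or baseline adjustment, although the same section already specifies a suitable model for its neighbour. The consequence is that a chance baseline difference carries into an informal comparison of arm means, by 0.023 to 0.092 log10 per 1-SD imbalance at SD 1.5, k = 1 and 340 per arm, and that precision available from a covariate already collected goes unused. All of these sizes rest on assumed SDs and correlations. No planned test, decision or conclusion changes, so this is a low-cost improvement and not a flaw in the confirmatory analysis.

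**What to change.** In SAP 4.3.2.2, add an ANCOVA of Day 8 log10 viral load in the Virology set, with the covariates already named for the AUC: treatment (500 mg IM vs 500 mg IV), baseline log10 viral load, age group and gender. Using change instead of the Day 8 value as the response gives the same treatment difference once baseline is in the model. Report the adjusted IM-IV difference in log10 copies/mL with a 95% CI, as supportive and outside the testing hierarchy. Keep the raw by-visit summaries and the baseline-band tables.

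The cost is a sentence in the SAP and one model on data and covariates already held, with no extra participants, procedures or alpha. If it is added after the Day 29 results are known, label it post hoc.

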Available data suggest that SARS-CoV-2 infection is associated with variable incubation period, dependent on factors such as the infecting variant, patient risk group and vaccination status. Studies conducted from the first phase of the pandemic in 2020 describe the median incubation period as greater than five days [[Lauer 2020](#)]. Further studies looking at the Delta variant estimate this period to be four days [[Grant 2022](#)]. Whilst epidemiological studies on the Omicron variant are still ongoing, early research suggests the median incubation period for this variant is approximately three days [[Brandal 2021](#); [Helmsdal 2021](#); [Jansen 2021](#)]. The median time to progression to severe disease (ICU admission/development of acute respiratory distress syndrome) from onset of symptoms has been estimated to be 12 days (range 8 to 15 days) with a median duration from onset to death or discharge of 21 days (range 17 to 25 days) [[Zhou 2020](#)]. In addition, viral loads are highest early in the course of disease and tend to fall once severe sequelae have ensued, although remain detectable by RT-PCR well into the course of disease [[Zhou, 2020](#); [Wölfel, 2020](#)]. The average duration of SARS-CoV-2 RNA shedding is estimated at 17·0 days in upper respiratory tract, 14·6 days in lower respiratory tract, 17·2 days in stool, and 16·6 days in serum samples [[Cevik, 2021](#)]. Notably, although viral nucleic acid can be detected well after symptom resolution in individuals with mild infection, shedding of infectious virus in sputum appears to be limited to the first week of symptoms [[Wölfel, 2020](#)].

These data suggest that early intervention with a potently neutralizing antibody prior to the onset of severe sequelae of disease may effectively prevent disease progression and hasten the resolution of disease. This study is warranted given that COVID-19 is considered a serious disease or condition - defined as a disease or condition associated with morbidity that has substantial impact on day-to-day functioning, and that may lead to more severe complications.

Throughout the pandemic, the SARS-CoV-2 virus has continued to mutate, resulting in new variants. Some of these variants emerge and disappear while others persist. Because new variants will continue to emerge, this substudy is designed to collect clinical safety data at higher dose(s) of sotrovimab.

VIR-7831  
Vir Biotechnology, Inc.

VIR-7831-5008 (GSK Study 217114)  
Amendment 4

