#### 5.1.2. Type of Participant and Disease Characteristics

3. Participants who have a positive SARS-CoV-2 test result within 7 days of randomization (by any validated diagnostic test e.g., RT-PCR, antigen-based testing on any specimen type)

AND

4. Oxygen saturation  $\geq 94\%$  on room air

AND

5. Have symptoms of COVID-19 defined by one or more of the following: fever, chills, cough, sore throat, malaise, headache, joint or muscle pain, change in smell or taste, vomiting, diarrhea, shortness of breath on exertion

AND

6. Participant to be dosed less than or equal to 7 days from onset of symptoms to dosing day (D1)

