4.2. Primary Endpoint Analyses

4.2.1. Definition of Primary Endpoint

The primary endpoint is the progression of COVID-19 through Day 29 as defined by hospitalization > 24 hours for acute management of illness due to any cause OR death.

The primary efficacy endpoint will primarily be assessed using an estimand that uses a hypothetical strategy to deal with the main intercurrent events as detailed in section 1.1.

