4.2.4. Sensitivity analyses

To assess the sensitivity of the results to the missing data, a tipping point analyses will be performed for the hypothetical and treatment policy estimands. The underlying response rate among those subjects with missing response status in each arm will be varied ranging between 0 and 1. This analysis will be two-dimensional, i.e. it will allow for assumptions about the assumed response rate (and thus missing outcomes) in the two treatment arms to vary independently. For combinations of the assumed response rates in the arms, the number of additional responders among subjects with missing response will be imputed multiple times by drawing from a binomial distribution. The absolute difference and associated standard error for each imputed dataset will be calculated using the primary analysis model and results combined using Rubin's rules to calculate the risk difference and the 95% CI for the treatment comparison. Results will be presented via a heatmap.

In addition, a summary of the number of COVID-19 progressions through Day 29 (as defined in section 4.2.1) for the hypothetical estimand will be provided for the split by those progressions that occur <3 days and ≥ 3 days post-dose.

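### The SAP's displays of serum concentration by progression status mix samples taken before and after the event, and the Day 29 samples are essentially all after it

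*SAP*

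**What the plan says.** SAP 4.3.2.2 adds two exposure displays to the secondary analyses. The first is a "Box plot of serum pharmacokinetic concentrations at Day 8, 15 and 29 vs COVID-19 progression status through Day 29". The second is a "Summary table of Day 8 serum pharmacokinetic concentrations (n, mean, SD, median, min, max) by COVID-19 progression status through Day 29". Both use the status derived for the hypothetical estimand, and both are to be shown by treatment group and for all groups together.

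The outcome, defined in SAP 4.2.1, is an acute hospital stay of more than 24 hours, whatever the reason, or death, up to Day 29. An event on any day up to Day 29 therefore puts a participant in the progressed group at every PK visit.

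Neither display has a landmark, a pre-event restriction, or a rule for participants who progressed before the draw. SAP 4.2.4 does consider event timing, in a count of progressions "split by those progressions that occur <3 days and ≥ 3 days post-dose", but that split is not applied to the PK displays. SAP 4.3.1.6 leaves further exposure-response work to a separate population PK plan.

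**The concern.** A reader will look at these displays to see whether participants with lower concentrations went on to progress more often. That reading needs the concentration to come first. Where the sample follows hospitalization, the level may also reflect the illness or its care. Progressors who died or missed the visit are absent, so a later box describes only those still sampled.

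These are the only exposure-progression displays that this SAP specifies, in a trial that compares an intramuscular with an intravenous route. Few progressors are expected, so a handful of post-event or missing samples can change the picture in either direction.

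**Working it through.** **Size of the progressed group.** SAP section 5 plans 340 per arm for about 90% power, with 2% progression in both arms, a 3.5% margin and one-sided 2.5%. Check: n = (1.960 + 1.282)² × 2 × 0.02 × 0.98 / 0.035² ≈ 336.2, rounded up to 337. At 340 the power is 90.3%, so the plan's figure reproduces. Expected progressors are 340 × 0.02 = 6.8 per arm.

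**Day 29.** The outcome window closes on Day 29, so every progressor has had the event by then. The only exception is the ±2-day visit window in SAP 4.1.1: a sample drawn on Day 27 or 28 could precede an event a day or two later.

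**Background timing.** Protocol 2.3.2 says that the median time from symptom onset to severe disease (ICU admission or ARDS) "has been estimated to be 12 days (range 8 to 15 days"). Protocol 5.1.2 has the "Participant to be dosed less than or equal to 7 days from onset of symptoms to dosing day (D1"), and SAP 4.2.2.1 carries the same criterion. With dosing s days after onset, the study day of the event is 12 − s + 1, with range 8 − s + 1 to 15 − s + 1:

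- s = 7: Day 6 (2 to 9)
- s = 5: Day 8 (4 to 11)
- s = 3: Day 10 (6 to 13)
- s = 0: Day 13 (9 to 16)

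**Share of samples on or after the event.** Let T be the study day of progression. The share over the three planned draws is [P(T ≤ 8) + P(T ≤ 15) + 1] / 3. The documents do not give the distribution of T, so every row below is an assumption.

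| Assumed timing | Day 8 | Day 15 | Day 29 | Three draws together |
|---|---|---|---|---|
| Background (triangular 8, 12, 15 days from onset; dosing uniform 0 to 7 days), simulated | 34% | 99.8% | 100% | 78% |
| Uniform over Days 2 to 29 | 7/28 = 25% | 14/28 = 50% | 100% | 58% |
| Exponential, median 3 days post-dose, cut at Day 29 | 80% | 96% | 100% | 92% |
| Exponential, median 15 days post-dose, cut at Day 29 | 38% | 66% | 100% | 68% |
| Extreme: all events on Days 16 to 29 | 0% | 0% | 100% | 33% |

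If 25% of post-event draws are missed, the last column becomes 72% (background) and 51% (uniform). If 50% are missed, it becomes 64% and 41%.

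**Carry-over of earlier exposure.** Protocol 2.2 gives a median half-life of 56.5 days (42.4 to 77.3; 500 mg IV, 9 participants). The decline from Day 8 to Day 29 is 1 − 2^(−21/56.5) = 23%, or 29% and 17% at the ends of that range.

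**Pooling the routes (secondary).** Protocol 1.1 reports progression of 2.7% (500 mg IM) and 1.3% (IV). With 340 per arm assumed, that is 9.2 and 4.4 events. IM then supplies 9.2/13.6 = 67.5% of progressors and 330.8/666.4 = 49.6% of non-progressors. Suppose there is no relationship within route, and IM concentrations are a fraction r of IV (r is not in the documents). The pooled progressor mean relative to the non-progressor mean is (0.675r + 0.325) / (0.496r + 0.504). That is 11.9% lower at r = 0.5 and 6.3% lower at r = 0.7.

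**The case against.** The strongest reply is that these are descriptive extras with no test, decision rule or causal statement attached. A time-ordered analysis may also sit in the population PK plan, which is not supplied. Both points limit the consequence, but neither puts the samples before the event in the outputs this SAP does specify.

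Four stronger readings are tempting and are not supported.

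- A reader might infer that most samples behind every display are post-event. The table uses Day 8 only, and on the background timing about two-thirds of Day 8 draws (66%) precede the event. For the three-day box plot, a majority is likely but not certain: it fails if events are late or many post-event draws are missed.
- A reader might infer that the displays show nothing. With a half-life near 56 days, a later level still partly reflects earlier exposure, although that figure is for IV dosing and says nothing about IM absorption or the effect of illness.
- A reader might take the 3-day split in SAP 4.2.4 as evidence that events come early. It is only a planned count.
- A reader might infer that route is shown to drive progression, so that the overall display is confounded. The adjusted IM minus IV difference in Protocol 1.1 is 1.11% (95% CI −1.24% to 3.45%), which includes zero. Displays within treatment group are already planned. The 6% to 12% pooling shift rests on an assumed concentration ratio and is of the same order as sampling error: with within-route CVs of 25.2% and 39.4% (the clearance and Cmax figures in Protocol 2.2), 13.6 progressors give a relative standard error of at least 25.2/√13.6 = 6.8% to 39.4/√13.6 = 10.7%.

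The timing evidence is also indirect. The background figure concerns ICU admission or ARDS, whereas the endpoint is hospitalization or death. Hospitalization normally comes first, so the post-event shares may be understated. The SAP rests on Protocol Amendment 3, which is not supplied; the supplied protocol describes the later substudy.

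**Conclusion.** The time order in both displays is uncontrolled, and this should be corrected. Day 29 is post-event in essentially every progressor, and that needs no timing assumption. Day 15 is probably mostly post-event: nearly all on the background timing and half if events are uniform. The Day 8 share is uncertain: about one-third on the background timing, 25% to 80% across the other timings tried, and zero only in the extreme case with no event before Day 16. Selective loss of progressors from the later boxes is not counted anywhere. The displays therefore cannot reliably show whether low exposure preceded progression. Mixing of routes in the overall display is a secondary point of unknown size. No primary, tested or safety conclusion depends on any of this.

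**What to change.** In SAP 4.3.2.2:

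1. At Day 8, for both the box plot and the table, include only participants alive and progression-free at the sample. Classify them by progression after the sample through Day 29. Where only dates are available, count a same-day event as preceding the draw.
2. Report by arm how many progressed, and how many died, before the draw.
3. State how this status relates to the hypothetical-estimand status now used. Under SAP 4.1.3 and 6.2.8, data after an intercurrent event are set to missing and multiply imputed, and the SAP does not say how an imputed status enters a box plot.
4. Drop the Day 29 panel from the progression comparison. Either landmark the Day 15 panel in the same way or label it as mainly post-event.
5. Read the displays within treatment group, as already planned. Stratify the overall display and the total by route, or label them as mixing routes.

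The cost is SAP wording and the programming of two outputs, with no new samples. The downside is small numbers. Of 6.8 expected progressors per arm, a Day 8 landmark keeps about 6.8 × 0.664 = 4.5 on the background timing, 6.8 × 0.75 = 5.1 if events are uniform, and 6.8 × 0.198 = 1.3 if they are early (median 3 days). At Day 15 almost none remain on the background timing. That is the information actually available there. If the outputs already exist (Protocol 1.1 quotes the Day 29 result), the landmark version can be added as a labelled supplement.
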